### **3.0 SUBJECT ELIGIBILITY**

#### **3.1 Inclusion Criteria**

Subjects must meet all of the inclusion criteria as listed below to participate in this study.

- 3.1.1 Histologically or cytologically confirmed colorectal adenocarcinoma, with unresectable metastatic or locally advanced disease documented on diagnostic imaging studies.
- 3.1.2 Previously received 1-2 prior lines of therapy. Subjects who relapse within 6 months of adjuvant chemotherapy comprised of oxaliplatin and a fluoropyrimidine will have their adjuvant therapy count as one prior line of therapy.
- 3.1.3 Confirmed wild-type in KRAS and NRAS codons 12, 13, 59, 61, 117, and 146; and BRAF codon 600, by standard of care testing of tumor specimen. Tissue used for testing may have been collected from primary or metastatic site.
- 3.1.4 Microsatellite stable as detected by PCR-based assay OR CLIA-certified sequencing methodology such as Foundation One; OR mismatch repair proficient as detected by immunohistochemistry showing intact nuclear staining of MLH1, MSH2, MSH6, and PMS2.
- 3.1.5 Radiographically measurable disease present per RECIST 1.1

- 3.1.6** Age  $\geq$  18 years at the time of consent.
- 3.1.7** Eastern Cooperative Oncology Group (ECOG) performance status 0 or 1.
- 3.1.8** Blood counts performed within 3 weeks prior to starting study therapy must have absolute neutrophil count  $\geq$  1,500/mm^3, platelets  $\geq$  100,000/mm^3, and hemoglobin  $\geq$  9 g/dL.

**\*Note:** Hematology and other lab parameters that are  $\leq$  grade 2 BUT still meet criteria for study entry are allowed. Furthermore, changes in laboratory parameters during the study should not be considered adverse events unless they meet criteria for dose modification(s) of study medication outlined by the protocol and/or worsen from baseline during therapy.

- 3.1.9** Liver function tests performed within 3 weeks prior to starting study therapy must have total bilirubin  $\leq$  1.5 x upper limit of normal (ULN), alanine aminotransferase and aspartate aminotransferase  $\leq$  3 x ULN, and albumin  $\geq$  2.5 g/dL.
- 3.1.10** Serum creatinine performed within 3 weeks prior to starting study therapy must be  $\leq$  1.5 x ULN, or have calculated creatinine clearance (using Cockcroft-Gault formula provided in Appendix 11.3) of  $\geq$  50 mL/minute.
- 3.1.11** Females of childbearing potential must have a negative serum pregnancy test within 24 hours prior to receiving the first dose of study medication. Females of childbearing potential must agree to use 2 methods of effective contraception or abstain from heterosexual sex throughout the treatment period and for 5 months after the last dose of study treatment. Females of childbearing potential are women who have not been surgically sterilized (have undergone a hysterectomy, bilateral tubal ligation, or bilateral oophorectomy) or have not been free of menses for  $>$ 1 year.
- 3.1.12** Male subjects with female partners must have had a prior vasectomy or agree to use an adequate method of contraception (i.e., double barrier method: condom plus spermicidal agent) starting with the first dose of study therapy through 6 months after the last dose of study treatment.
- 3.1.13** Written informed consent and HIPAA authorization for release of personal health information. NOTE: HIPAA authorization may be included in the informed consent or obtained separately.
- 3.1.14** An adequate amount of archival tumor tissue must be available at baseline to be eligible for enrollment in the study. If archival tissue is not available or is inadequate, then the subject must consent to undergo a mandatory biopsy at baseline in order to participate in the study.

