**Editorial and Therapy Changes:**

1. For section 1.6, a paragraph regarding stool specimen collection and rationale for addition of a stool specimen was added to this section.
2. For section 2.3, exploratory objective 2.3.5 was added which states “To collect stool specimens to assay gut microbial composition at baseline and longitudinally.”
3. For inclusion criterion 3.1.4, “OR CLIA-certified sequencing methodology such as Foundation One” was added as an additional method for Microsatellite stable detection.
4. For section 4.1.1, the sample size was adjusted for accuracy.
5. For section 4.3.1 and 4.3.2, an infusion window of +/- 15 minutes was added for the panitumumab, nivolumab and ipilimumab infusions.

6. For section 4.4.1, the following adverse reaction criteria pertaining to the dosing delays/dose modifications criteria for panitumumab were inadvertently omitted from the

table and have been added: Infusion-related reactions; Dermatologic reaction; Pulmonary Fibrosis/ILD.

7. For section 4.4.2, “+/- Ipilimumab” was added to the section header.
8. For section 4.4.2, the following adverse reaction terms and the corresponding severity and dose modification were added to the table: Adrenal insufficiency; Myocarditis; Infusion Related Reaction; Uveitis, eye pain, blurred vision. Additionally, the following adverse reaction terms were inadvertently omitted and have been added to the table: Colitis; Pneumonitis; Hypophysitis; Type 1 Diabetes Mellitus; Nephritis and Renal Dysfunction; Rash; Encephalitis; Other.
9. For section 4.4.2, footnotes b, c, d, e and f were added to the table.
10. For section 4.4.2.1, “and/or Ipilimumab” was added.
11. For section 4.4.2.1, the following terms were inadvertently omitted and have been added to the table under column heading “Baseline Liver Function Test (NCI-CTCAEv4.03 grade)”: AST or ALT normal; AST or ALT 1.1 to  $\leq 2.5$  X ULN (Grade 1); Total Bilirubin normal; Total Bilirubin 1.1 to  $\leq 1.5$  X ULN (Grade 1).
12. For section 4.4.2.2, dose delay criteria for ipilimumab was added to this section and duplicate criteria was removed as this criteria has been incorporated into sections 4.4.2 and 4.4.2.1.
13. For section 4.4.2.3, “+/- Ipilimumab” was added to the section header.
14. For section 4.4.2.4, section header revised to include immune related events for ipilimumab.
15. Section 4.4.3 and subsections 4.4.3.1, 4.4.3.2 were deleted as this was a duplication of information.

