### **3.2 Exclusion Criteria**

- 3.2.1** Past treatment with an antibody targeting EGFR including cetuximab or panitumumab.
- 3.2.2** Past treatment with an antibody targeting immune checkpoints including CTLA-4, PD-1, PD-L1, PD-L2, or CD137.
- 3.2.3** Known untreated brain metastasis or brain metastasis treated within 3 months prior to enrollment in this trial.
- 3.2.4** Has evidence of interstitial lung disease or active, non-infectious pneumonitis.
- 3.2.5** Has a known additional malignancy that is active and/or progressive requiring treatment; exceptions include basal cell or squamous cell skin cancer, in situ cervical or bladder cancer, or other cancer for which the subject has been disease-free for at least five years.
- 3.2.6** Treatment within 21 days of the first dose of study drug with any other chemotherapy, immunotherapy, biologic therapy, vaccine therapy, or investigational treatment for the treatment of malignancy, or failure to recover from adverse effects of prior therapies administered over 4 weeks prior to Study Day 1. All toxicities from prior therapies must be  $\leq$  Grade 1 (or  $\leq$  Grade 2 for alopecia or peripheral neuropathy). Prior systemic treatment in the adjuvant setting is allowed. See note above under inclusion 3.1.8
- 3.2.7** Any serious and/or unstable pre-existing medical disorder (aside from malignancy exception above), psychiatric disorder, or other conditions that could interfere with subject's safety, obtaining informed consent, or compliance to the study procedures.
- 3.2.8** Pregnant or planning to become pregnant within 6 months after the end of treatment. (NOTE: breast feeding and storage of breast milk is not allowed while mother is being treated, and for up to 5 months after stopping nivolumab, 2 months after stopping panitumumab and/or ipilimumab.
- 3.2.9** History of organ allograft or other history of immunodeficiency, or is receiving systemic steroid therapy or any other form of immunosuppressive therapy within 7 days before the first dose of investigational treatment.
- 3.2.10** Inability or unwillingness to comply with study and/or follow-up requirements.
- 3.2.11** Any major surgery, extensive radiotherapy, chemotherapy with clinically significant delayed toxicity, biologic therapy, or immunotherapy within 21 days

[figure not shown]
October 01,,

2020  
prior to randomization and/or daily or weekly chemotherapy without the potential for delayed toxicity within 14 days prior to randomization.

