**4.4.2.1 Nivolumab and/or Ipilimumab Dose Modifications/Delays for Liver Toxicity**

Recognizing that mCRC is often associated with the presence of liver metastases at baseline, the following criteria will be used for dose modifications/delays of nivolumab and/or ipilimumab for liver toxicity.

Baseline Liver Function Test (NCI-CTCAEv4.03 grade)	Adverse Reaction Severity	Dose Modification *
AST or ALT normal	AST or ALT $\geq 3$ X ULN to $\leq 5$ X ULN	Withhold dose a
	AST or ALT $> 5$ X ULN	Permanently discontinue
AST or ALT 1.1 to $\leq 2.5$ X ULN (Grade 1)	AST or ALT $\geq 5$ X ULN to $\leq 8$ X ULN	Withhold dose a
	AST or ALT $> 8$ X ULN	Permanently discontinue
Total Bilirubin normal	$> 1.5$ to $\leq 3$ X ULN	Withhold dose a
	$> 3$ X ULN	Permanently discontinue
Total Bilirubin 1.1 to $\leq 1.5$ X ULN (Grade 1)	$\geq 3$ to $5$ X ULN	Withhold dose a
	$> 5$ X ULN	Permanently discontinue

a) Resume treatment when adverse reaction returns to Grade 0 or 1. If toxicity persists  $> 6$  weeks, permanently discontinue nivolumab +/- ipilimumab

\* For additional management, including monitoring and use of corticosteroids or additional immunosuppressant therapies, recommend using guidelines for management of immunotherapy related toxicities, primarily the NCCN Management of Immunotherapy-Related Toxicities Version 1.2020. Section 11.2 has algorithms for possible management of selected toxicities, but management does not have to follow direction of Section 11.2.

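### Eligibility admits AST/ALT up to 3 x ULN, but the mandatory liver dose table stops at a baseline of 2.5 x ULN, leaving the highest eligible baselines with no AST/ALT hold threshold in the table and an unclear stop threshold

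*Combined protocol and SAP*

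**What the plan says.** **Entry.** Section 3.1.9 caps "alanine aminotransferase and aspartate aminotransferase" at 3 x ULN and total bilirubin at 1.5 x ULN. The note under 3.1.8 says that laboratory values no worse than "grade 2 BUT still meet criteria for study entry are allowed". Exclusion 3.2.6 limits toxicities from prior therapies to Grade 1 in general, and ends with "See note above under inclusion 3.1.8".

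**Dosing.** Section 4.4.2.1 gives its reason for a separate liver table: "mCRC is often associated with the presence of liver metastases at baseline". The first column is headed "Baseline Liver Function Test (NCI-CTCAEv4.03 grade" and has these rows:

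| Baseline | Hold (x ULN) | Stop (x ULN) |
|---|---|---|
| AST or ALT normal | 3 to 5 | > 5 |
| AST or ALT 1.1 to 2.5 (Grade 1) | 5 to 8 | > 8 |
| Bilirubin normal | > 1.5 to 3 | > 3 |
| Bilirubin 1.1 to 1.5 (Grade 1) | 3 to 5 | > 5 |

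The hepatitis row of Section 4.4.2 only points to this table, and Section 4.4.2.4 describes 4.4.2 and 4.4.2.1 as the mandatory dosing guidance. Section 4.4.2.5 repeats the AST/ALT stops for a normal baseline (> 5) and a Grade 1 baseline (> 8), without a range for Grade 1.

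**Resuming.** Footnote a of 4.4.2.1 says "Resume treatment when adverse reaction returns to Grade 0 or 1" and discontinues after 6 weeks. Section 4.4.2.3 also accepts a return to the baseline value.

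**Outside guidance.** The asterisk note under the table recommends the NCCN guideline and mentions the Section 11.2 algorithms, "but management does not have to follow direction of Section 11.2".

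**The concern.** The table is meant to give each subject AST/ALT limits suited to where that subject started. As printed, it omits the highest AST/ALT baselines that eligibility allows. Those are the subjects for whom a baseline-adjusted rule matters most, since raised enzymes from liver metastases are the table's stated reason.

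For such a subject, a hold for rising AST/ALT would rest on generic rules and the investigator's judgment. Sites could reasonably differ on whether to stop above 5 x ULN, above 8 x ULN, or only at Grade 4. Section 8.3 counts events that call for discontinuation under Section 4.4 towards the accrual-suspension boundary, so an unclear stop could also make that count depend on the site. That effect cannot be quantified from the documents.

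**Working it through.** The plan states no figure to reproduce. The check compares the eligible range with the table's range and then looks for any other rule that fills the difference.

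**1. Width of the gap at the upper end** (eligibility ceiling in 3.1.9 minus top of the highest baseline row in 4.4.2.1)
- AST/ALT: 3.0 - 2.5 = 0.5 x ULN
- Bilirubin: 1.5 - 1.5 = 0

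Bilirubin serves as the control: there the table reaches the eligibility ceiling exactly. Item 11 of the earlier amendment's change list, which begins "AST or ALT normal; AST or ALT 1.1 to", prints the same 2.5, so a text-extraction error is unlikely.

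**2. Who is clearly affected.** The rows say AST *or* ALT, so a subject with one enzyme in the band may fall into a row through the other enzyme. The clear case is both enzymes above 2.5 and up to 3 x ULN. Take two subjects who each rise to 6 x ULN:
- Both enzymes at 2.4 at baseline (6/2.4 = 2.50-fold): in the Grade 1 row, and 6 lies between 5 and 8, so dosing is held.
- Both enzymes at 2.8 at baseline (6/2.8 = 2.14-fold): in no row, so the table requires no hold.

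**3. Whether another rule supplies the number**
- The 4.4.2.5 stop above 8 x ULN applies only if a baseline of 2.5 to 3 counts as Grade 1. The only range the text attaches to Grade 1 AST/ALT is 1.1 to 2.5, and the CTCAE cut-offs are not reproduced.
- The hold for other Grade 3 reactions in 4.4.2 is not reliable here, because footnote b exempts isolated laboratory abnormalities without clinical significance.
- The Grade 4 stop, the recurrence and persistence stops, the substantial-risk stop, the bilirubin rows and the investigator-judgment hold all remain. None gives a numeric AST/ALT hold short of Grade 4.
- Section 11.2 and NCCN guidance is advisory, so whatever it says cannot supply a mandatory threshold.
- Exclusion 3.2.6 limits prior-therapy toxicity only. It does not exclude enzyme elevation from metastases.

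**4. Fold rise to reach each threshold** (threshold divided by baseline)

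| Case | Hold | Stop, above |
|---|---|---|
| Printed row at its limit, 2.5 | 5/2.5 = 2.00 | 8/2.5 = 3.20 |
| Row extended to 3, baseline 2.6 | 5/2.6 = 1.92 | 8/2.6 = 3.08 |
| Row extended to 3, baseline 3.0 | 5/3.0 = 1.67 | 8/3.0 = 2.67 |
| One enzyme at 2.6, other normal (literal normal row) | 3/2.6 = 1.15 | 5/2.6 = 1.92 |
| One enzyme at 3.0, other normal (literal normal row) | 3/3.0 = 1.00 | 5/3.0 = 1.67 |

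If one enzyme is at 2.6 to 3.0 and the other at 1.1 to 2.5, the literal row is the Grade 1 row, and the figures equal those of the extended row. Under the literal normal row, a subject entering at exactly 3.0 already meets the hold threshold on day 1. Borrowing that row is therefore no workable substitute.

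**5. Resuming.** If Grade 1 ends at the printed 2.5, a subject who returns to a baseline of 2.8 fails footnote a of 4.4.2.1 but satisfies 4.4.2.3.

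**The case against.** The strongest reply is that the table itself shows Grade 1 was meant to reach 3 x ULN. For bilirubin, the normal-baseline hold begins just above 1.5, where the Grade 1 row ends. By the same structure, the AST/ALT normal-baseline hold begins at 3, so Grade 1 should end near 3. The column is headed by CTCAE grade, and 4.4.2.3, 4.4.2.5 and footnote c of 4.4.2 all speak of baseline grade. On that reading the stop above 8 x ULN covers these subjects and 2.5 is a slip in one cell. This is plausible, and it is why the stop is called unclear rather than absent. It remains inference against a printed number, and it leads to the same correction.

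Other points stand in part:
- The backstops are real, and chemistries are drawn at every dosing visit. A Grade 3 transaminase rise on two checkpoint inhibitors may well be judged clinically significant, and so be held despite footnote b. That depends on judgment, which the table was written to replace.
- Read strictly, baselines above ULN but below 1.1 x ULN also have no row, for bilirubin as well as AST/ALT. This is true but trivial: it does not affect the comparison at the upper end.
- Once Grade 1 is stated to reach 3 x ULN, adding baseline to footnote a changes nothing for these subjects. That edit is only for consistency.
- The reach is small and no harm is shown. This is accepted.

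**Conclusion.** The concern holds. The AST/ALT rows of the mandatory liver table stop 0.5 x ULN short of the eligibility ceiling. For a subject with both enzymes above 2.5 and up to 3 x ULN, the table gives no AST/ALT hold threshold, and the stop depends on an undefined use of Grade 1.

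The conclusion rests on the printed 2.5 being the true content of the cell. If Grade 1 was intended to reach 3 x ULN, the stop is covered and the cell is simply wrong.

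The practical reach is limited. No baseline AST/ALT distribution is given, so the number affected is unknown. It is probably small, because both enzymes must lie in a narrow band and a drug-related rise must follow. The primary response analysis and the sample size are unaffected. It is still worth correcting, because the number governs a safety decision and costs almost nothing to change.

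**What to change.** In Section 4.4.2.1, change the upper AST/ALT baseline row to run from 1.1 to 3 x ULN (Grade 1). Keep the hold at 5 to 8 x ULN and the stop above 8 x ULN. In Section 4.4.2.5, state the same range where Grade 1 AST/ALT is used. As a minor consistency edit, let footnote a of 4.4.2.1 also accept a return to baseline, to match 4.4.2.3.

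The cost is one table cell, one line in 4.4.2.5 and two words in a footnote, which can go into the next amendment. Eligibility, sample size and analysis do not change. Lowering the entry limit to 2.5 x ULN would also close the gap, but it would narrow eligibility for no other benefit.

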### **3.2 Exclusion Criteria**

- 3.2.1** Past treatment with an antibody targeting EGFR including cetuximab or panitumumab.
- 3.2.2** Past treatment with an antibody targeting immune checkpoints including CTLA-4, PD-1, PD-L1, PD-L2, or CD137.
- 3.2.3** Known untreated brain metastasis or brain metastasis treated within 3 months prior to enrollment in this trial.
- 3.2.4** Has evidence of interstitial lung disease or active, non-infectious pneumonitis.
- 3.2.5** Has a known additional malignancy that is active and/or progressive requiring treatment; exceptions include basal cell or squamous cell skin cancer, in situ cervical or bladder cancer, or other cancer for which the subject has been disease-free for at least five years.
- 3.2.6** Treatment within 21 days of the first dose of study drug with any other chemotherapy, immunotherapy, biologic therapy, vaccine therapy, or investigational treatment for the treatment of malignancy, or failure to recover from adverse effects of prior therapies administered over 4 weeks prior to Study Day 1. All toxicities from prior therapies must be  $\leq$  Grade 1 (or  $\leq$  Grade 2 for alopecia or peripheral neuropathy). Prior systemic treatment in the adjuvant setting is allowed. See note above under inclusion 3.1.8
- 3.2.7** Any serious and/or unstable pre-existing medical disorder (aside from malignancy exception above), psychiatric disorder, or other conditions that could interfere with subject's safety, obtaining informed consent, or compliance to the study procedures.
- 3.2.8** Pregnant or planning to become pregnant within 6 months after the end of treatment. (NOTE: breast feeding and storage of breast milk is not allowed while mother is being treated, and for up to 5 months after stopping nivolumab, 2 months after stopping panitumumab and/or ipilimumab.
- 3.2.9** History of organ allograft or other history of immunodeficiency, or is receiving systemic steroid therapy or any other form of immunosuppressive therapy within 7 days before the first dose of investigational treatment.
- 3.2.10** Inability or unwillingness to comply with study and/or follow-up requirements.
- 3.2.11** Any major surgery, extensive radiotherapy, chemotherapy with clinically significant delayed toxicity, biologic therapy, or immunotherapy within 21 days

[figure not shown]
October 01,,

2020  
prior to randomization and/or daily or weekly chemotherapy without the potential for delayed toxicity within 14 days prior to randomization.

- 3.2.12 Known immediate or delayed hypersensitivity reaction or idiosyncrasy to drugs chemically related to study drug.
- 3.2.13 Known Human Immunodeficiency Virus (HIV), Hepatitis B virus (HBV), or Hepatitis C virus (HCV) infection. Subjects with laboratory evidence of cleared HBV and HCV infection will be permitted.
- 3.2.14 Active autoimmune disease requiring systemic treatment in the past 3 months (for example with disease modifying agents, corticosteroids, or immunosuppressive drugs). Replacement therapy (eg, thyroxine, insulin, or physiologic corticosteroid replacement therapy for adrenal or pituitary insufficiency, etc.) is not considered a form of systemic treatment. Subjects with vitiligo or resolved childhood asthma/atopy would be an exception to this rule. Subjects that require intermittent use of bronchodilators, local steroid injections, or inhaled or topical steroids would not be excluded from the study. Subjects with hypothyroidism stable on hormone replacement or Sjogren's syndrome will not be excluded from the study.
- 3.2.15 Active infection requiring intravenous systemic therapy.

## 4.0 TREATMENT PLAN

### 4.1 Schema

#### 4.1.1 Rationale for Doses Selected

We plan to perform a single-arm, open-label, multicenter Phase II clinical trial of nivolumab 240 mg IV q2wk, ipilimumab (1 mg/kg IV q6wk), and panitumumab (6 mg/kg IV q2wk), after a safety lead-in cohort of a total of 6 subjects has completed 12 weeks of combination therapy at the proposed starting doses. The starting doses and schedule were carefully selected after consideration of existing clinical studies and preclinical data. The efficacy of ipilimumab monotherapy is dose-dependent, but the rate and severity of immune-related adverse events is also dose-dependent. The FDA-approved dose of combination ipilimumab and nivolumab in management of metastatic melanoma is ipilimumab 3 mg/kg IV q3wk for four doses combined with nivolumab 1 mg/kg IV q3wk; followed by nivolumab monotherapy 240 mg flat dose IV q2wk. Notably, studies of combination ipilimumab and nivolumab have started both antibodies concurrently, with the rationale that preclinical models showed that the combination is synergistic only when administered concurrently rather than sequentially, and so we plan to administer the investigational drugs concurrently as well. Subsequent clinical trials have investigated combinations of ipilimumab and nivolumab that would attenuate the frequency and severity of immune-related adverse events without mitigating efficacy. The efficacy and toxicity profiles of more infrequent dosing of ipilimumab combined with nivolumab were studied in a phase I study in subjects with chemotherapy-naïve recurrent stage IIIB or IV NSCLC, CheckMate 012. In this study, treatment with ipilimumab 1 mg/kg q6wk combined with nivolumab 3 mg/kg q2wk was much better tolerated than treatment with ipilimumab 1 mg/kg q3wk combined with nivolumab 3 mg/kg q3wk. Additional dosing combination regimens tested revealed inferior efficacy when nivolumab dosing was decreased to 1 mg/kg. Treatment with ipilimumab 1 mg/kg q6wk combined with nivolumab 3 mg/kg q2wk resulted in a 33% rate of grade 3-4 treatment-related AEs, but only 13% rate of treatment-related AEs leading to study drug discontinuation (compared to 19% grade 3-4 treatment-related AEs and 10% treatment-related AEs leading to discontinuation in nivolumab 3 mg/kg IV q2wk arm). The FDA has determined that based on population pharmacokinetics models, there is a negligible difference in overall exposure between nivolumab 240 mg IV q2wk and 3 mg/kg IV q2wk. Consequently, we plan the ipilimumab and nivolumab dosing within safety cohort 1 to be ipilimumab 1 mg/kg IV q6wk plus nivolumab 240 mg IV q2wk. The dose of panitumumab selected within dose level 1 is the FDA-approved monotherapy dose.

If DLTs occur in no more than one subject in the first 6 subjects treated during the 12 week assessment period in the first safety cohort, then the trial would continue enrolling subjects to the remainder of the first stage of the phase II portion to complete enrollment to 32 subjects to assess efficacy of panitumumab, ipilimumab and nivolumab (3-drug combination). This would then be followed by interim analysis to determine whether the second stage would merit enrollment. If the 3-drug combination is not well tolerated, then 6 additional subjects will be enrolled into safety cohort 2 and receive panitumumab and nivolumab (2-drug combination). If no more than one subject experiences a DLT in safety cohort 2, then the trial will continue enrolling subjects into the phase II portion and the 2-

October 01,,  
2020

drug combination of panitumumab and nivolumab will be evaluated efficacy. Subjects may continue combination treatment as long as they are benefitting from therapy until disease progression, unacceptable toxicity or withdrawal for other reasons as deemed necessary by the investigator.

DLT definitions applicable to the safety assessment run-in are defined in section 4.2. Subjects will undergo disease evaluation every 6 weeks for the first year, and will continue on this disease assessment schedule if they are at least stable but have less than a CR. If subjects continue on study after one year with a CR, then disease evaluations may occur every 12 weeks from that point forward.

